### 5.1.1.2 Overall Survival (OS)

OS is defined as the time from randomization to the date of death from any cause:

[OS = death date – randomization date + 1].

Any subject without a date of death in the database at the time the survival analyses are performed will be censored at the date of last known alive. The date of death is recorded on the death report form page. The last known alive date is defined as the last date the subject was known to be alive at the study. The last known alive date will be the latest date among the following:

- Last assessment date among, e.g., vital signs assessment, performance status assessment, tumor imaging, and assessment date in third-party data such as central laboratory, ECG etc.
- Last adverse events date
- Last known alive date collected on the 'Long-term Follow-up' page of eCRF
- Date of last contact in 'End of Study' page of the eCRF

- Last date among last study treatment, and last concomitant medications, subsequent interventions administered after study treatment discontinuation.

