## 7.2 Handling of Dropouts or Missing Data

In order to achieve the goal of a well-conducted clinical study according to Good Clinical Practice, every effort will be made to collect all data. However, despite best efforts, it may be inevitable that some data may be missing or incomplete.

In the subject data listing all available data, including partial data, will be presented as they are recorded on the case report forms (CRFs).

Time to event or duration of event endpoints will be calculated based on the study day of the event date (or censoring date) rather than visit number or visit label. Missing efficacy or safety data will not be imputed unless otherwise specified.

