### 7.2.1 Partial Dates for Adverse Events

For adverse events (AEs) with partially missing start dates, it's necessary to impute an AE start date to define TEAE. For the partial date of AE start date (missing day and/or month and/or year), the following imputation rules will be applied:

- If year of the AE start date is missing, no date imputation will be made and the AE will not be considered treatment-emergent unless the investigator has deemed it to be treatment-related.
- If both day and month of the AE start date are missing but year is known, the day and month will be imputed with the day and month of the first study dose date if the year is equal to the year of first dose. Otherwise, the month and day is imputed as the first day of the year (01 Jan).
- If only day is missing, and if the year and month are equal to the first dose date, the day will be imputed as day of the first dose date. Otherwise, the day will be imputed as "01."

Partial AE end dates will be imputed for non-ongoing AEs as follows:

- If year of the AE end date is missing, no date imputation will be made.
- If both day and month of the AE end date are missing but year is known, the date of the last dose of study drug will be used as the end date of the AE. Otherwise, December 31 will be used as the end of the AE.
- If only day is missing, the date of last dose of study drug will be used as the end date of the AE. Otherwise, the last day of the month will be used as the end of the AE.

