### 7.2.2 Partial Dates for Concomitant Medication

For concomitant medications (CM) with incomplete dates, imputation will be used to convert to a complete date. Imputed dates will be used to determine Study Day.

Partial medication start dates will be imputed as follows:

- If year of the CM start date is missing, no date imputation will be made.
- If both day and month of the CM start date are missing but year is known, the day and month will be imputed with the day and month of the first study dose date if the year is equal to the year of first dose. Otherwise, the month and day is imputed as the first day of the year (01 Jan).
- If only day is missing, and if the year and month are equal to the first dose date, the day will be imputed as day of the first dose date. Otherwise, the day will be imputed as “01.”

Partial medication end dates will be imputed for non-ongoing medications as follows:

- If year of the CM end date is missing, no date imputation will be made.
- If both day and month of the CM end date are missing but year is known, the date of the last dose of study drug will be used as the end date of the medication. Otherwise, December 31 will be used as the end of the medication.
- If only day is missing, the date of last dose of study drug will be used as the end date of the medication. Otherwise, the last day of the month will be used as the end of the medication.

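### The SAP's partial end-date rules for AEs and medications assign the last-dose date without a condition, so an imputed end can precede its start or leave the recorded month or year

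*SAP*

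**What the plan says.** SAP 7.2.1 covers partial AE end dates for events that are not ongoing.

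- Day missing: "If only day is missing, the date of last dose of study drug will be used as the end date of the AE". The next sentence reads "Otherwise, the last day of the month will be used as the end of the AE".
- Day and month missing, with the year recorded: "the date of the last dose of study drug will be used as the end date of the AE. Otherwise, December 31 will be used" (continuing as the AE end).
- Year missing: nothing is imputed.

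SAP 7.2.2 repeats the scheme for medications: "If only day is missing, the date of last dose of study drug will be used as the end date of the medication", again followed by an 'Otherwise'. It adds: "Imputed dates will be used to determine Study Day".

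The start-date rules in the same two sections are conditional. The day-missing rule for AEs opens "If only day is missing, and if the year and month are equal to the first dose date", and the rule for a missing day and month requires the year to equal that of first dose. SAP 7.2 sets the default: "Missing efficacy or safety data will not be imputed unless otherwise specified".

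**The concern.** An 'Otherwise' needs an 'if' before it. In the start-date rules the 'if' is present. In the four end-date rules (two for AEs, two for medications) it is not, so the alternative can never be reached and every partial end with a known year becomes the last-dose date. No rule stops the imputed end from preceding the start, or from contradicting the month or year that the site did record.

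The trial's schedule makes such records likely. Protocol 6.4.7.1 collects AEs for at least 30 days after last dose. Protocol Table 2 marks medication recording in the Post-treatment and Long-term Follow-up columns. Protocol 5.7 records medications taken within 60 days of Day 1, some of which will have stopped before dosing began.

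At stake are the AE durations that SAP 8.3.1 and Protocol 7.8 require in listings, and the Study Day of medication ends.

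**Working it through.** The plan states no figure on this point, so there is none to reproduce. The check applies the rules to dates.

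**Rules compared, day missing.** L is the last-dose date, S the start, E the true end (only its month and year are known).

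- (a) As written: imputed end = L.
- (b) With the condition that 'Otherwise' implies: imputed end = L if E and L share year and month, else the last day of E's month.
- (c) As (b), but not before the start: imputed end = max(S, result of (b)).

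**Worked dates.** Assume Day 1 = 15 January 2019. Boosts follow Day 92 at 8-week intervals (Days 148, 204, 260, 316), and Day 316 is 26 November 2019 = L.

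| Record (end day missing) | True E − S | (a) imputed end | (a) end − S | (b) imputed end |
|---|---|---|---|---|
| AE 6 Dec to 21 Dec 2019 | 15 days | 26 Nov 2019 | −10 days | 31 Dec 2019 |
| AE 5 Feb to 12 Feb 2019 | 7 days | 26 Nov 2019 | 294 days | 28 Feb 2019 |
| Medication 10 Mar to 20 Apr 2021 | 41 days | 26 Nov 2019 | −470 days | 30 Apr 2021 |
| Medication 1 Dec to 20 Dec 2018 | 19 days | 26 Nov 2019 | 360 days | 31 Dec 2018 |

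In all four rows the as-written end falls outside the recorded month. The 2021 medication row relies on Table 2; Protocol 6.4.5 describes a shorter recording window. Even that window can run past the last dose.

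**Is the condition alone enough?** No. Take L = 5 November 2019 and an AE from 15 to 22 November. Month and year match L, so (b) gives 5 November, 10 days before the start. Rule (c) gives 15 November.

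**How often.** Enumerate AEs starting 1 to 30 days after last dose, lasting 0 to 30 days, over 365 last-dose dates: 30 × 31 × 365 = 339,450 combinations, equally weighted. That weighting is an assumption, not trial data. Share with an imputed end before the start:

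- (a) 100%, which also follows directly, since L < S for every such event
- (b) 16.6%
- (c) 0%

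**What uses the end date.** TEAE status depends on onset (SAP 5.2.1 and 7.2.1). The prior/concomitant split depends on start date (SAP 8.3.7). No table listed in SAP 8.3.1 summarises duration. This leaves the listed AE duration and the medication end Study Day.

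**The case against.** The strongest reply is that the intent is plain. A programmer who sees 'Otherwise' will supply the condition by analogy with the start-date rules. SAP 7.2 also has listings show partial dates as recorded, so a reader can see the raw entry, and nothing tabulated rests on an end date.

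Much of this stands: the consequence is small, and the documents give no count of affected records. Two parts do not stand. First, the condition has to be guessed, and the obvious guess still leaves 16.6% of the enumerated post-dose AEs ending before they start. Second, showing the raw partial date does not correct a duration or Study Day derived from the imputed one.

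A reader might also go further and infer that these rules put artificial dates into OS and TTNT censoring, because SAP 5.1.1.2 lists "Last adverse events date" and last concomitant medication among the sources for the last-known-alive date. The documents do not support that:

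- Section 5.1.1.2 takes the latest date from a list that already includes last study treatment. Adding another copy of the last-dose date cannot move that maximum; the shift is 0 days in every case checked.
- December 31 and month end occur only in the 'Otherwise' branch, which is never reached on the literal reading. One cannot use the literal reading for negative durations and the inferred one for late censoring.
- The default in SAP 7.2 is no imputation, and section 5.1.1.2 speaks of when the subject was known to be alive. The uses stated for imputed dates are defining TEAEs (AE starts) and Study Day (medications).

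What remains is that section 5.1.1.2 does not say in so many words whether imputed AE or medication dates count.

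**Conclusion.** The point holds as a drafting error in SAP 7.2.1 and 7.2.2. As written, every record that starts after last dose and has an imputable partial end is given an end before its start. Every record that ended in an earlier month (day missing) or earlier year (day and month missing) is extended to last dose, outside what was recorded. An event that began during dosing but ended in a later month is cut short at last dose.

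The size is minor: listed AE durations, assuming they are computed from imputed ends, and medication end Study Days. TEAE status, the prior/concomitant classification and the primary and secondary analyses are unaffected. The number of records affected cannot be estimated from the documents.

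**What to change.** Replace the end-date rules in SAP 7.2.1 and 7.2.2 with: if only the day is missing and the year and month equal those of last dose (or, if day and month are missing, the year equals that of last dose), use the last-dose date; otherwise use the last day of that month (or December 31 of that year); the imputed end may not precede the start date or fall after death or data cutoff.

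The last clause is needed as well as the condition, as the 5 November example shows.

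Optionally, add to SAP 5.1.1.2 that imputed AE and medication end dates are not used for the last-known-alive date. Once the rule is repaired, month-end and December 31 dates can occur, so the sentence would prevent differing readings.

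Cost: SAP wording and the matching derivation specification. No change to the protocol, data collection or sample size.

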### 7.2.2 Partial Dates for Concomitant Medication

For concomitant medications (CM) with incomplete dates, imputation will be used to convert to a complete date. Imputed dates will be used to determine Study Day.

Partial medication start dates will be imputed as follows:

- If year of the CM start date is missing, no date imputation will be made.
- If both day and month of the CM start date are missing but year is known, the day and month will be imputed with the day and month of the first study dose date if the year is equal to the year of first dose. Otherwise, the month and day is imputed as the first day of the year (01 Jan).
- If only day is missing, and if the year and month are equal to the first dose date, the day will be imputed as day of the first dose date. Otherwise, the day will be imputed as “01.”

Partial medication end dates will be imputed for non-ongoing medications as follows:

- If year of the CM end date is missing, no date imputation will be made.
- If both day and month of the CM end date are missing but year is known, the date of the last dose of study drug will be used as the end date of the medication. Otherwise, December 31 will be used as the end of the medication.
- If only day is missing, the date of last dose of study drug will be used as the end date of the medication. Otherwise, the last day of the month will be used as the end of the medication.

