5.7 Concomitant Therapy

Except for excluded medications ([Section 5.8](#)), medications for symptoms and supportive management are permitted. During the study, if the use of any concomitant treatment becomes necessary (e.g., for treatment of an AE), the treatment must be recorded on the source document and eCRF, including the reason for treatment, name of the drug, dosage, route, and date of administration. All medications including prescription, over-the-counter (OTC), herbal, and other nutritional vitamins and/or supplements taken within 60 days of Day 1 will be recorded on the eCRF.

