## **5.2 Safety Endpoints**

### **5.2.1 Adverse Events**

A treatment-emergent adverse event (TEAE) is defined as any AE that newly appeared or worsened in severity following initiation of the study treatment administration until 30 days after last dose of the study treatment. In addition, all study treatment related AEs are treated as TEAE.

Medical Event of Interest (MEOI) is defined as selected non-serious AEs are classified as MEOIs, refer to protocol section 6.4.7.5 for more details.

Immune-mediated event --

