### **8.3.7 Prior and Concomitant Medications**

All concomitant medications and prior medications will be coded to therapeutic drug classes and generic drug names using the World Health Organization (WHO) Drug Classification. The incidence of prior and concomitant medication usage will be summarized by treatment arm, by therapeutic drug class, and generic drug names on safety set separately.

**Concomitant medication** is any medication with start date on or after the initial dosing of study treatment.

**Prior medication** is defined as any medication with start date on or before the first day of study treatment, or medication with start date missing.

Each subject will be counted once only for each therapeutic drug class, generic drug names, and for the overall summary.

Prior and concomitant therapies will also be presented in data listings.

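### Partial start dates are set to the first-dose date even when the recorded end date shows that the drug or event ended before dosing

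*SAP*

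**What the plan says.** SAP 7.2.2 has two start-date rules that can place a medication on the first-dose date. When day and month are missing and the start falls in the calendar year of first dosing, "the day and month will be imputed with the day and month of the first study dose date"; in any other year, 01 January is used. With only the day missing, the first-dose day is used when month and year match; otherwise day 01. SAP 7.2.1 has the same pair for adverse events, for example "if the year and month are equal to the first dose date, the day will be imputed as day of the first dose date", and gives the reason that it is "necessary to impute an AE start date to define TEAE". None of these rules refers to an end date. The end-date rules in the same sections act only on partial end dates, so a complete end date before dosing stands as recorded.

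The start date then decides the table. Under SAP 8.3.7 a concomitant medication "is any medication with start date on or after the initial dosing of study treatment", and a prior medication "is defined as any medication with start date on or before the first day of study treatment, or medication with start date missing". The two definitions overlap on the first dosing day. SAP 5.2.1 takes a TEAE to be "any AE that newly appeared or worsened in severity following initiation of the study treatment administration until 30 days after last dose" and adds all treatment-related AEs; Protocol 7.8 counts onset on or after the start of treatment.

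Pre-dose drugs will be in the database: Protocol 5.7 has medications "taken within 60 days of Day 1 will be recorded on the eCRF", and Table 1 collects them at Screening.

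**The concern.** Defaulting an unknown start to the first dose is a usual cautious choice when the timing relative to dosing is unknown. It is not cautious when the record itself settles the timing. If the end date is before dosing, the start must be too, and the imputed value contradicts collected data.

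The population makes such drugs likely. Day 1 falls within 28 days of the last first-line dose or of the last day of local regional therapy (Protocol 3.1.3, with the possible screening extension in 3.3), so supportive medication that stopped before Day 1 is to be expected. At stake is the accuracy of the concomitant-medication table and, to a much smaller degree, of the TEAE tables.

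**Working it through.** The plan states no figure that depends on this rule, so there is none to reproduce. The check applies the rules as written to test records, then asks how often the calendar condition is met.

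**Test records** (assumed first dose 20 Jun 2018):

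| Recorded start | Recorded end | Imputed start | Start minus end | Table under SAP 8.3.7 |
|---|---|---|---|---|
| 2018 | 31 May 2018 | 20 Jun 2018 | +20 days | concomitant and prior |
| Jun 2018 | 12 Jun 2018 | 20 Jun 2018 | +8 days | concomitant and prior |
| May 2018 | 31 May 2018 | 01 May 2018 | none | prior only |
| 2017 | 31 May 2018 | 01 Jan 2017 | none | prior only |

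The first two records are wrong; the last two are not. The inversion can reach 364 days in the year-only case (end 01 January, dose 31 December) and 30 days in the day-missing case (end on the 1st, dose on the 31st). If either of the first two were an AE, its onset would be the first-dose date, and it would be a TEAE under Protocol 7.8.

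**Calendar match.** Assumptions: first-dose dates uniform over a 365-day year, start k days before dosing, k uniform on the stated range.

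- Same year: P = 1 − mean(k)/365. For k = 1 to 60, 1 − 30.5/365 = 0.916. For k = 22 to 60, 1 − 41/365 = 0.888.
- Same month: in a month of L days, L − k dose days have a start k days earlier in that month (none if k ≥ L). For k = 1 to 60 the total is Σ L(L−1)/2 = 7×465 + 4×435 + 378 = 5,373, and 5,373/(365×60) = 0.245. For k = 22 to 60 it is Σ (L−22)(L−21)/2 = 7×45 + 4×36 + 21 = 480, and 480/(365×39) = 0.034.

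These shares cover all drugs started before dosing, including those that continue past Day 1, for which the rule does no such harm.

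**Restricted to drugs that ended before dosing.** This needs a duration, which the documents do not give. With start 1 to 60 days before dosing and duration 1 to 14 days (both assumed), a simulation of 200,000 draws gives about 91% misclassified if only the start year is known and about 17% if only the start day is missing.

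**With the fix.** The first record gets 01 Jan 2018 and the second 01 Jun 2018. Both become prior only and, as AEs, not treatment-emergent. The other two are unchanged.

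**The case against.** Several points on the other side are sound and limit the finding.

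- *Few pre-dose AEs exist to misclassify.* Protocol Table 1 has no AE row, and the AE row of Table 2 starts at Day 1. Conditions found at screening go to medical history (Protocol 6.4.7.2). Between Main Study consent and Day 1 only procedure-related SAEs and hospitalizations are recorded (6.4.7.3). Protocol 6.4.7 says collection runs from enrollment, but Table 2 places enrollment at Day 1, with Day 1 procedures within 72 hours of randomization. The AE part survives only for these records.
- *The drug is not lost from the prior table.* Because the definitions overlap on Day 1, the error is one extra entry.
- *No inference is touched.* PFS, OS and the tested secondary endpoints do not use these dates. The rule is the same in both arms of a blinded trial.
- *Listings keep the data as recorded* (SAP 7.2), so a reader of the listing can see the true end date. The tables would still be wrong.

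A programmer might add the missing check unasked, but the SAP exists to pre-specify the handling and states that it prevails over the protocol (SAP 9). An unwritten check would depart from it.

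A reader might infer that the rule makes restricted drugs, such as growth factors or immunosuppressive corticosteroids, appear as on-study violations. The documents do not support that. SAP 8.3.7 counts subjects by class and generic name and says nothing of prohibited use; corticosteroid restrictions depend on dose and route, which such a row does not show; and SAP 8.1.2 leaves deviations to clinical-team review, with no derivation from imputed dates.

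**Conclusion.** The rule as written is wrong for one class of record: a partial start whose known part matches the first-dose year, or year and month, with a recorded end before first dose. Such a drug is wrongly added to the concomitant table; such an AE, which will be rare, would be counted as a TEAE. The effect is confined to descriptive medication and safety tables.

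Its size in the trial cannot be stated. It would be tempting to read 92% and 25% as misclassification rates. They are calendar-match shares, conditional on a partial start date, and the documents give neither the frequency of partial dates nor the share of those drugs that ended before dosing. For drugs started 22 to 60 days before dosing the shares are 89% and 3%, so with only the day missing the problem is small. The high figures need a year-only start paired with an informative end date.

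Two readings of the SAP are assumed. First, imputed starts feed the classification in SAP 8.3.7: section 7.2.2 mentions only study day, but 8.3.7 gives separate treatment only to a missing start. Second, an onset imputed to the first-dose date counts as treatment-emergent. The SAP's TEAE wording could mean strictly after first dose, but SAP 7.2.1 imputes the onset for this very purpose, and Protocol 7.8 includes the first-dose date.

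**What to change.** Add to SAP 7.2.1 and 7.2.2:

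- Impute a partial start to the first-dose date only if the end date is missing, ongoing, or could fall on or after first dose. Otherwise impute the earliest date consistent with the recorded part of the start and not after the recorded end.
- Judge this on the end date as recorded, before any end-date imputation. A partial end date counts as before dosing when its latest possible date is before first dose, and it is then not imputed to the last study dose.
- Records known to have ended before first dose are neither concomitant nor treatment-emergent, except AEs that SAP 5.2.1 counts as TEAEs because they are related to study treatment.

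The second item is needed because the current end-date rules can send a partial end date to the last dose of study drug. Without it, a drug with an end recorded as February and a first dose in March would be declared finished before dosing yet carry an imputed end on treatment.

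The cost is a few sentences in two SAP sections, a condition in the start-date program and a matching exception in the end-date program, before database lock. No data collection changes.
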